Script development. We will develop the prototype script following the focus group discussions with non-participating LHWs, and initially refine the script through training and retraining of the study LHWs.

Oral testing offer. LHWs will provide routine household contact investigation services, including TB education, screening, sputum collection, HIV testing, and clinic referral, according to routine public health protocols. In purposively selected households and following the prototype invitation script, LHWs will offer oral HIV testing first to the household member statistically most likely to accept (e.g. oldest female), then to other eligible adults and adolescents using the FDA-approved OraQuick ADVANCE rapid HIV-1/2 antibody test.

Iterative, experience-based interviews. A social scientist will privately interview members of 20 purposively sampled households, including households in which all eligible members accepted HCT during TB contact investigation, and households in which some or all did not accept HCT. We will prompt each household member to recount their decision process, describe their primary social ties and sources of social support, complete short stigma scales, and suggest changes to the prototype script and other aspects of how testing is offered. We will collate these data and adapt intervention components after every 5 households.

TB Stigma: We will conduct a cross-sectional study nested within the Aim 1 procedures to describe the prevalence and characteristics of TB stigma in a population of households living with a TB patient. This will be achieved by distributing validated parallel Van Rie stigma scales (*Van Rie TB-HIV-related stigma scales, attached.*) to approximately 120 household contacts in approximately 40 consecutive households. The parallel Van Rie stigma scale is a scale that measures both TB and HIV/AIDS related stigma. The scale is structured to capture stigma related to these key domains: fear of transmission and disease, values and attitudes associated with shame, blame and judgments, and disclosure of disease status. These scales have been validated in a variety of settings and have excellent internal consistency, good construct validity, and moderate test-retest reliability.

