To further explore the relationship between perceptions of TB and attitudes toward TB evaluation, we will interview 5 low and 5 high TB-stigma scoring individuals from the parallel Van Rie stigma scales. During the study visits described above, the stigma scales will be scored immediately, eligible respondents identified, and eligible respondents invited to a 45-minute interview. If the invitation is accepted, the interview will be preferentially conducted during the same household visit, although if time or space concerns make this infeasible or unacceptable, the interview may be rescheduled to a different time and location as specified or agreed to by the participant. In addition to stigma scale score, participants will be purposively selected to ensure variation by age and gender among interviewees.

These interviews will be conducted by a trained social scientist fluent in both English and Luganda in order to conduct interviews in the language of preference for the participants.

The comparison between TB stigma scores and TB evaluation outcomes will be analyzed using a bivariate analysis. TB evaluation outcomes include whether the participant successfully completed sputum collection and/or if they completed a clinic follow-up if indicated by the health care worker.

COVID Health Worker Cohort: We will also establish a prospective cohort of COVID-engaged health workers to longitudinally evaluate the psychosocial and physiological impact of COVID-19 response on health workers involved in TB units. Our aim is to learn more about health worker stress, burnout and the impact these things may have on HIV-TB services and the health system as a whole.

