Measures. We will assess perceptions of stigma within the household using a pair of validated, comprehensive, parallel scales designed to assess perceived/attributed stigma for HIV and TB that we have adapted to the household level.(61) (*Van Rie TB-HIV-related stigma scales, attached.*) We will measure composite household stigma by pooling the measures of perceived and enacted stigma from all members of the household. We will collect individual age, gender, occupation (if applicable), income (if applicable), education in years, relationship to index patient, history of testing for HIV, month and year of last test, and self-reported symptoms of TB (including cough, subjective fever, or weight loss). We will collect measures of household stability, including household tenure in years.

Sample size. We will deliver the script and interview contacts from 20 households (approximately 40-60 individuals). In most studies, 10-15 subjects per group are required to reach saturation, the point at which interviews do not yield new themes.(62,63) We will carry out ≥ 2 FGDs with 15 experienced LHWs. For TB stigma related questions, we will distribute the stigma scale up to 40 households

(approximately 100-120 individuals). We will attempt to build a cohort of between 60 and 100 health care workers from around Uganda engaged in HIV and TB care during and after the COVID pandemic. Due to the changing nature of the pandemic and the changing staffing requirements for clinics, this number may change.

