This protocol presents minimal risks to the subjects and Unanticipated Problems Involving Risks to Subjects or Others (UPIRSOs), including adverse events, are not anticipated. In the unlikely event that such events occur, Reportable Events (which are events that are serious or life-threatening and unanticipated (or anticipated but occurring with a greater frequency than expected) and possibly, probably, or definitely related) or Unanticipated Problems Involving Risks to Subjects or Others that may require a temporary or permanent interruption of study activities will be reported immediately (if possible), followed by a written report within 5 calendar days of the Principal Investigator becoming aware of the event to the IRB (using the appropriate forms from the website) and any appropriate funding and regulatory agencies.

The investigator will apprise fellow investigators and study personnel of all UPIRSOs and adverse events that occur during the conduct of this research project through 1) weekly study meetings carried out via teleconference during and immediately following the data collection period, or 2) via email as they are reviewed by the principal investigator. The protocol's research monitor(s), Fogarty International Center of NIH (sponsor/funder) and the relevant IRB of Makerere University (local collaborator/host) will be informed of any UPIRSO, including adverse events, or Reportable Event within 5 days of the event becoming known to the principal investigator.

13. Statistical Considerations: Describe the statistical analyses that support the study design.

Aim 1 is a formative qualitative study to refine an intervention; it is not designed for statistical tests. Based on the findings of the formative study described here, the study team will specify the final intervention and submit a modification to this protocol for a pilot study evaluating that intervention.

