In the Aim 2 analysis, we will calculate and compare uptake across each of the trial arms using an intention-to-treat analysis. We will also consider a per protocol analysis and model adjusted for imbalances in baseline confounders as secondary analyses. To test the hypothesis that a norming intervention can increase test uptake, we will compare testing uptake among the intervention households and control households using cluster-adjusted chi-squared tests of proportion and by fitting mixed effects logistic regression models with two levels (household, contact.) To test the hypothesis that invitation scripts that apply acceptance-optimized sequencing of oral test offers and prosocial messaging can decrease HIV stigma within households, we will evaluate change in HIV-TB stigma using cluster-adjusted dependent t-tests and fitting multilevel models with clustered standard errors. We will conduct a causal mediation analysis to determine to what degree the effects of the intervention on stigma explain the improvement in test uptake using observed-variable structural equation modeling. All hypothesis tests will be carried out at alpha of 0.05, corrected for multiple tests as appropriate. We will report household ICC for stigma as well as test uptake and will consider a household ICC of >0.2 a sufficient level of clustering necessitating adjustment.

SECTION II: RESEARCH INVOLVING DRUGS, BIOLOGICS, RADIOTRACERS, PLACEBOS AND DEVICES

If this section (or one of its parts, A or B) is not applicable, check off N/A and delete the rest of the section.

A. RADIOTRACERS N/A

B. DRUGS/BIOLOGICS N/A

B. DEVICES N/A

SECTION III: RECRUITMENT/CONSENT AND ASSENT PROCEDURES**1. Targeted Enrollment: Give the number of subjects:**

- a. Targeted for enrollment at Yale for this protocol: 0
- b. If this is a multi-site study, give the total number of subjects targeted across all sites:
 - 40 to 60 individuals drawn from 20 households (Aim 1)
 - Approximately 8 to 15 lay health workers with experience carrying out TB contact investigation
 - Approximately 60-100 health workers participating in HIV and TB care services during the COVID-19 pandemic
 - Approximately 152 index patients and their approximately 304 household contacts (Aim 2)

2. Indicate recruitment methods below. Attach copies of any recruitment materials that will be used.

 Flyers	 Internet/web postings	 Radio

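### The nested Aim 1 comparison of TB stigma with TB evaluation is planned only as a bivariate analysis, with no stated adjustment for household clustering

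*Combined protocol and SAP*

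**What the plan says.** Section I.4, Procedures for Aim 1 (TB Stigma), describes a cross-sectional survey nested in Aim 1, covering "approximately 120 household contacts in approximately 40 consecutive households". The Aim 1 sample-size paragraph gives the number as "approximately 100-120 individuals" in up to 40 households. The analysis is one sentence, which says that "TB stigma scores and TB evaluation outcomes will be analyzed using a bivariate analysis". The outcomes are individual and yes/no: "whether the participant successfully completed sputum collection and/or if they completed a clinic follow-up if indicated by the health care worker". No test, standard error, interval or treatment of households is named.

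The plan handles clustering openly elsewhere. For Aim 2, the Analysis paragraph of Section I.4 and Section I.13 both specify cluster-adjusted tests and multilevel models. Section I.13 adds that the team "will consider a household ICC of >0.2 a sufficient level of clustering necessitating adjustment". Within Aim 1, the interview analysis will estimate how far the acceptability responses correlate within households.

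**The concern.** Contacts in one household are not independent observations. They share an index patient, a visit and the lay health workers who carry it out. The protocol's background also argues that stigma is produced within groups and that home HIV testing decisions are made by households. The usual bivariate tools (t-test, chi-squared test, correlation) assume independent observations. If both the stigma score and the outcome are alike within households, those tools count too much information.

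At stake is the interval around the association between TB stigma and completing TB evaluation. It would be too narrow, and a chance association would be somewhat more likely to be reported as a finding.

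**Working it through.** **Inputs from the documents**
- 120 contacts in 40 households gives m = 120/40 = 3 per household; 100 in 40 gives m = 2.5.
- The only household ICC stated is 0.59. It comes from Aim 1 data and is for consent to HIV testing (Aim 2 Sample Size).
- The threshold for adjustment is an ICC above 0.2 (Section I.13).

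**Assumptions, because the documents are silent:** household ICCs for TB stigma and for TB evaluation each between 0.2 and 0.59; equal cluster sizes; all contacts contribute; two-sided 5% test.

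**Step 1. The plan's own figure.** The Aim 1 comparison has no stated precision. The only calculation that uses a household ICC is the Aim 2 sample size: 152 households at m = 2 and 138 at m = 3. With proportions 0.85 and 0.98, 90% power and two-sided 5%, the pooled two-proportion formula gives

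n = [1.960 × √(2 × 0.915 × 0.085) + 1.282 × √(0.1275 + 0.0196)]² / 0.13² = 94.6 contacts per arm.

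Multiply by 1 + (m − 1) × 0.59 and divide by m:
- m = 2: 94.6 × 1.59 / 2 = 75.2, so 76 households per arm, 152 in total.
- m = 3: 94.6 × 2.18 / 3 = 68.8, so 69 per arm, 138 in total.

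Both figures are reproduced. (Rounding n up to 95 first gives 152 and 140.) So 0.59 enters as an ordinary design-effect ICC for consent to HIV testing.

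**Step 2. Design effect for the Aim 1 comparison.** For an association between two variables that both vary within households, the variance inflation is

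D = 1 + (m − 1) × ICC(stigma) × ICC(outcome).

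The correct standard error is √D times the unadjusted one, the effective sample is n/D, and the true error of a nominal 5% test is 2 × [1 − Φ(1.96/√D)].

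With m = 3 and n = 120:

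| ICC stigma, ICC outcome | D | SE factor | Effective n | True error | Simulated |
|---|---|---|---|---|---|
| 0.2, 0.2 | 1.08 | 1.04 | 111 | 5.9% | 6.5% |
| 0.2, 0.59 | 1.24 | 1.11 | 97 | 7.8% | 8.2% |
| 0.59, 0.59 | 1.70 | 1.30 | 71 | 13.2% | 12.9% |

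The last column is a null simulation of the unadjusted test: 6,000 runs, 40 households of 3, a continuous score against a binary outcome with prevalence 0.5.

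**Step 3. Upper bound.** A score constant within each household has ICC 1. Then D = 1 + 2 × 1 × 0.59 = 2.18, the SE factor is 1.48, effective n is 55 and the true error is 18.4%.

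**Step 4. Smaller clusters.** At m = 2.5 (100 contacts), both ICCs at 0.2 give D = 1.06 and 5.7%; both at 0.59 give D = 1.52 and 11.2%. Clinic follow-up counts only where it was indicated. If that left two contacts per household, both ICCs at 0.59 would give D = 1 + 0.59² = 1.35 and about 9.1%.

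**Step 5. Does the remedy work with 40 households?** In the same simulation, simple cluster-robust errors had a true error of 6.0% with no clustering, 6.5% and 6.6% in the first two rows of the table, and 7.1% in the third. That removes much of the inflation where it is large but not all of it, hence the small-sample correction proposed below.

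**The case against.** The strongest reply is that the protocol promises no test here. Section I.13 states that "Aim 1 is a formative qualitative study to refine an intervention; it is not designed for statistical tests", the survey's declared purpose is descriptive, and no alpha, power or decision rule is attached to the comparison. This stands in part: it makes the point minor and supports an exploratory label. It does not dispose of it. That sentence describes a qualitative study, while this is a numerical comparison of scores with outcomes, and any interval or p-value reported would carry the error.

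Two stronger readings are tempting, and the documents do not support them.
- A reader might infer that the plan breaks its own rule on clustering. The 0.2 rule is conditional, refers to ICCs for stigma and HIV test uptake, and sits in the paragraph that opens "In the Aim 2 analysis, we will calculate and compare uptake across each of the trial arms using an intention-to-treat analysis". The 0.59 is for consent to HIV testing, not for sputum collection, clinic follow-up or TB stigma. Nothing shows that this comparison exceeds the threshold.
- A reader might infer that the plan specifies an analysis that ignores clustering. Bivariate means two variables. The plan's own Aim 2 cluster-adjusted chi-squared test shows that a two-variable comparison can carry a cluster adjustment. The text leaves the matter open.

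Nor is 18% a fair central figure. The Measures paragraph does plan a pooled household stigma score, but the TB-stigma text scores individuals and picks low- and high-scoring individuals for interview. It does not say that this comparison uses the pooled score.

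**Conclusion.** The concern holds as a minor point of analysis specification. The comparison is clustered by design and, unlike the Aim 2 analyses, has no stated cluster adjustment. Run as an ordinary bivariate analysis, its standard errors would need multiplying by about 1.04 to 1.30, and a nominal 5% test would have a true error of about 6% to 13%. Those ranges rest on assumed ICCs of 0.2 to 0.59 for both variables and three contacts per household. At the low end the effect is close to negligible. The comparison is neither a primary nor a secondary outcome of the Aim 2 trial, so that result is untouched.

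**What to change.** In the TB Stigma text of Section I.4:
- Name a household-clustered method for the binary outcomes: logistic GEE clustered on household with a small-sample correction, or logistic regression with a random household intercept.
- Report the intervals from that model, and the household ICCs for TB stigma and for each TB evaluation outcome.
- Describe the comparison as exploratory.

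The cost is slightly wider intervals and minor analysis work. No new data are needed; household membership only has to be carried into the analysis file.

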Aim 1: To develop a complex intervention to increase uptake of testing for HIV among household members by reducing perceptions of stigma associated with HIV and testing for HIV. Lay health workers (LHWs) will deliver a novel invitation strategy for HIV testing in 20 purposively sampled households that includes 1) acceptance-optimized sequencing, 2) prosocial messaging, and 3) salivary HIV testing. We will administer HIV and TB stigma scales before and after the invitation. We will interview all household members following the visit and engage LHWs in focus group discussions to explore feasibility and acceptability of the invitation strategy. We will iteratively refine the intervention to optimize acceptability and reductions in perceived stigma, for evaluation in Aim 2.

Aim 2: To evaluate the intervention on household HIV stigma and uptake of testing among household members undergoing TB contact investigation in a household-randomized pilot trial. We will recruit a prospective cohort of multiple-contact households undergoing routine contact investigation for TB. Households will be randomized to one of two study arms. Households in the control arm will receive routine household contact investigation services, including free, optional oral HIV testing. Households in the intervention arm will receive routine household contact investigation services and free, optional oral HIV testing with the social-behavioral framing intervention. LHWs in the intervention arm will use acceptance-optimized sequencing of invitations and a prosocial invitation script to offer salivary testing for HIV to household members. We will measure our co-primary outcomes of HIV and TB stigma using standardized instruments before invitation and after completion of post-test counseling. We will measure the proportion consenting to HIV testing, yield of HIV diagnoses, and the proportion of new PLWH linked to HIV care at 1 month and reassess household HIV and TB stigma at 3 months in a subset of participating households. Participants may also be contacted at a later point for interviews, focus-group discussions or surveys to better understand the implementation and impact of the intervention.

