LHWs will carry out home visits in pairs or with 3 LHWs dependent on the needs of that household. A LHW employed by the clinics will provide routine contact investigation services and a trained study LHW will collect research data and deliver the intervention for those randomized to the intervention arm of the study. While the LHW carries out standard contact investigation screening, the study LHW will administer a short HIV-TB stigma scale individually to all consenting adult members of the household in both arms. The research LHW will follow the assigned script based on randomization allocation to identify household members who are eligible and invite them to test for HIV, recording time-stamped offers, test decisions, and test results. The research LHW will collect household- and individual-level demographic, socioeconomic data, stigma scales, measures of household stability, including household tenure in years as well as relationship to and perceived influence of household members and clinical data using a structured survey.

Procedures for all households: Upon arrival, the CHWs will enroll all eligible, consenting household contacts in the study. But before doing this, at the start, CHWs will introduce themselves and ask for introduction of contacts. At this time the master list of all the contacts will be created.

- They will introduce the reason for their visit and the services they will offer (TBCI, oral HIV testing) using the introductory script for either Intervention or Routine Contact Investigation households, depending on the household assignment.
- For the intervention arm, one CHW will take the index case to a private area to ask the influence questions using the paper form (master list) as a key. After completing this exercise, the CHW will then embark conducting household contact screening interviews followed by HIV testing and any other study related activities. All data will be collected via CommCare.
- Meanwhile, the other CHW will be conducting routine TB contact investigation activities and any other clinical procedures in household TB contact investigation. Details of these procedures are found below:

a) Index case influence questions

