Randomization: For aim 2 of the study, variable block randomization will be done at the level of the household and will be performed at the time of household enrollment. Block sizes will have a minimum of 2, a maximum of 6. We will utilize study randomizer, an online randomization tool with concealed randomization. When a CHW has deemed an index patient and their household to be eligible for the study, and after the index patient or their guardian has provided verbal informed consent, the CHW will place a phone call to the study coordinator. The study coordinator will then enroll the household using the study randomizer tool and let the CHW know the study allocation. The CHW will then fill in the appropriate allocation, along with the randomization ID, and contact the appropriate CHW team for the household visit.

Households randomized to intervention group will be offered oral testing with the social-behavioral intervention. Households randomized to the standard of care group will be offered oral testing without any social-behavioral intervention. CHWs will operate in teams that are always assigned to the same arm of the study. There will be three teams of CHWs in total: one intervention group, one standard of care group, and one clinic-based group that will always be in charge of initial enrollment of index patients and recording any clinic follow up by individuals in either arm of the study.

Integrated intervention. In Intervention Households only, the CHW will present the opportunity to test using the script and procedures described in the next section (“Specification of intervention components”). This script communicates that the individual is completely free to opt out of testing, but that testing is the norm. We will use “Opt-Out” testing language along with language letting them know that they can decline.

If the household contact decides to opt out of HIV testing, the CHW will carry out a survey. These questions will take approximately the same amount of time as HIV testing and counselling procedures (~20 to 30 minutes) in order to blind other household members from the testing decision of that household contact. Contact decisions to test or not to test as well as test results will be recorded in CommCare.

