TB and HIV stigma scales Study CHWs will individually administer the short-form HIV-TB stigma scales to all study participants regardless of group using the CommCare application alongside a visual aid. These scales have a total of 13 items and were validated in the Uganda setting as part of the Aim 1 procedures. The scales will be administered first at the beginning of the home visit, then again at its conclusion. Each time, the CHW will briefly orient the participant to the response categories using a visual aid.

Documentation and Data management All enrollment procedures, household contact interviews and HIV testing details will be collected using CommCare. All forms will be available within a customized CommCare application that prevents common errors (such as not filling out a question etc.). Quality control procedures will include review of all study data collection forms for completeness and accuracy, including quality assurance testing of all validation and skip logic within the application, prior to study initiation. The US study coordinator will initiate reports on missing data and provide feedback to all study team members on the quality of quantitative data. All changes will be recorded using a data management google doc tracking sheet that contains information on the change, who made the change and a link directly to the location of the change on CommCare. Any duplicate cases (i.e. two cases for one index patient or contact) will be archived and similarly recorded.

Follow-up interview. At 3 months, the study LHW or a member of study team will contact a subset of households to schedule a follow-up visit or phone call if a second visit is unable to occur. The study LHW or a member of the study team will re-administer stigma scales to each participating member. Household members who are not present at the second household visit will be contacted by telephone to schedule a follow-up interview.

Sample Size.

During aim 2, we will distribute the stigma scales up to approximately 152 households containing approximately 304 household contacts with approximately 1:1 randomization (half in each study arm). We analyzed power for a 2-arm household-randomized, controlled trial using mixed models tests for two proportions in a two-level hierarchical design (household, contact). The assumptions and parameters within these calculations were based on data from Aim 1 and include:

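### In Aim 2 the study health-worker role that makes the arm-specific HIV test offer also administers the self-reported primary stigma scale, so a response shift that differs by arm cannot be told apart from reduced stigma

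*Combined protocol and SAP*

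**What the plan says.** All of this is in Section I, item 4 (Research Plan, Procedures for Aim 2) unless noted.

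- **Tasks of the study worker.** Under the household-randomized trial heading, a clinic-employed worker does routine contact investigation, while "a trained study LHW will collect research data and deliver the intervention for those randomized to the intervention arm of the study". The same paragraph adds: "the study LHW will administer a short HIV-TB stigma scale individually to all consenting adult members of the household in both arms". On the test offer it says: "The research LHW will follow the assigned script based on randomization allocation to identify household members who are eligible and invite them".
- **Who gives the scales, second statement.** Under TB and HIV stigma scales: "Study CHWs will individually administer the short-form HIV-TB stigma scales to all study participants regardless of group".
- **Timing.** The same heading says: "The scales will be administered first at the beginning of the home visit, then again at its conclusion". Aim 2 in item 1 says: "We will measure our co-primary outcomes of HIV and TB stigma using standardized instruments before invitation and after completion of post-test counseling".
- **Teams.** Under Randomization: "CHWs will operate in teams that are always assigned to the same arm of the study". Under CHW Training, all study workers first meet together to go over the aims and the design.
- **Three months.** Under Follow-up interview, for a subset of households: "The study LHW or a member of the study team will re-administer stigma scales to each participating member".
- **Status of the outcome.** The Analysis paragraph makes change in perceived HIV-TB stigma the primary outcome and test uptake the secondary one.

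**The concern.** Stigma is measured by asking people, face to face, how they perceive attitudes to HIV and TB. Answers to such questions can move towards what the interviewer seems to want. Between the two askings, intervention contacts receive an offer that presents testing as the norm and as something done for the household. Control contacts receive a standard opt-in offer. If the person who made the offer then repeats the scale, any wish to please that person is stronger, or at least different, in one arm. The interviewer also knows the arm and the aim of the trial.

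What is at stake is the interpretation of the primary outcome. A favourable arm difference could be less stigma, a courtesy response, or an interviewer effect, and the design as written cannot separate them. The same score feeds the mediation analysis in item 13, which asks how far stigma reduction explains test uptake, so a reporting shift would carry into that result too.

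**Working it through.** **1. Setting the passages side by side.**

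| Question | What the protocol provides |
|---|---|
| Who makes the test offer? | Study (research) worker, using the script for the arm |
| Who gives the scale? | Study worker, both arms |
| When? | Start and end of the same visit; the second after post-test counselling |
| Does the worker know the arm and the aims? | Yes; teams are fixed by arm and taught the aims |
| Does the script differ by arm? | Yes; prosocial and opt-out wording in the intervention arm only |
| Is the assessor masked or independent, or is the scale self-completed? | Not described |
| Is there an analysis by interviewer or for reporting bias? | None in the Analysis paragraph or item 13 |

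**2. Does the opening score solve it?** Let a respondent's score be true stigma plus a reporting component. A reporting component that is equal at both times cancels in the change. One created by the script, after the opening score, does not. The arm-specific introduction is also listed on arrival, ahead of the screening interviews, so the opening score may not be wholly free of arm-specific contact.

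**3. Do the other safeguards solve it?** Identical interview content and the visual aid standardise the questions, not the person asking. The one masking step described hides a contact's testing decision from other household members. The 3-month score covers a subset, and the study worker may take it.

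**4. The plan's own figure.** The 152 households are sized on uptake. A two-sided 0.05 test of 0.85 against 0.98 with 90% power needs 95 contacts per arm. With two contacts per household and ICC 0.59, 95 × 1.59 / 2 = 75.5, rounded up to 76 households per arm, or 152 in all. The figure reproduces and this point does not change it. No sample size is given for stigma.

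**5. Illustration of size.** *From the documents:* 152 contacts per arm in households of two, alpha 0.05. *Assumed:* all contacts give both scores; the test is two-sided; the household ICC of the stigma change lies between 0.1 and 0.59 (0.59 is the uptake value); the differential shift is b, in SDs of the change score; there is no true effect.

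Effective n per arm = 152 / (1 + ICC): 138.2 at 0.1 and 95.6 at 0.59. SE = √(2 / effective n): 0.120 and 0.145. Chance of a significant result = Φ(b/SE − 1.96) + Φ(−b/SE − 1.96).

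| Assumed shift b | ICC 0.59 | ICC 0.1 |
|---|---|---|
| 0.1 SD | 11% | 13% |
| 0.2 SD | 28% | 38% |
| 0.3 SD | 55% | 70% |

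For scale, the true difference detectable with 90% power is (1.96 + 1.28) × SE, or 0.39 to 0.47 SD.

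**6. Interviewer variation, illustrative only.** Assume two interviewers per arm (76 contacts each) and an interviewer ICC on the change score of 0.01 to 0.05. Net of household clustering, the variance of an arm mean is multiplied by (1 + household ICC + 74 × interviewer ICC) / (1 + household ICC). At household ICC 0.59 this is 2.33 / 1.59 = 1.47 to 5.29 / 1.59 = 3.33. The protocol fixes neither the number of interviewers nor either ICC for stigma.

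**The case against.** The strongest case on the other side has four parts.

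- **Shared bias.** Control workers also make an offer, counsel and then ask the scale, so part of any courtesy effect is common to both arms. This stands: only the differential part matters, and nothing in the documents sizes it.
- **A stable interviewer cancels.** If one person gives both scales, that person's constant effect drops out of the change score. This stands, and it is a reason not to move the closing scale alone to someone else. It does not deal with a shift that the script itself creates.
- **Fixed teams have a purpose.** Keeping teams to one arm plausibly limits contamination. This stands, and the fix leaves the teams as they are.
- **It is a pilot.** Uptake, on which the sample size rests, is recorded behaviour and less exposed. But stigma is the declared primary outcome, and item 1 says the data will inform a later randomized study. Item 3 (Background) itself criticises earlier stigma trials for weak methods.

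A reader might also infer more than the text supports. The protocol assigns the scale to a role; with two or three workers present, it does not say outright that one individual makes the offer and asks the closing questions. It places the closing scale at the end of the visit, after counselling, and the test result alone takes at least 20 minutes, so a gap of a few minutes cannot be assumed. The request to share one's decision so that others may be encouraged to test goes only to a first-invited contact who agrees to test, not to every intervention respondent.

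**Conclusion.** The concern holds as a weakness of design. The role that makes the arm-specific offer also collects the self-reported primary outcome, in arm-fixed teams that know the aims, and nothing planned addresses a response shift that differs by arm. A favourable result on stigma could not be attributed to the intervention with confidence.

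Its size and direction are unknown. The significance rates of 28% to 38% for a 0.2 SD shift rest on an assumed shift and an assumed stigma ICC; they show what such a bias could do, not that it is present. The interviewer variance figures are illustrative in the same way. A reader might infer that the trial will produce a false positive on stigma; the documents do not support that. The uptake comparison and its sample size are unaffected. The change is worth making before enrolment because it is cheap and concerns the primary outcome.

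**What to change.** 1. Under the household-randomized trial heading and under TB and HIV stigma scales, state that in both arms the visiting worker who does **not** make the HIV test offer gives **both** the opening and the closing scale. Interviewer and mode then stay the same within each change score. Reassigning the closing scale alone would mix two interviewers in one change.
2. Under Follow-up interview, state that in both arms the 3-month scale is given by a study-team member who is not told the allocation and did not visit the household. The text already allows a study-team member. Report this score as a check on the end-of-visit result. It covers a subset and may be taken by telephone, so it is not a replacement.
3. Record the assessor ID with every score. State as a limitation that home-visit assessors remain tied to arm and unmasked: the second worker belongs to the same team and is present for the arm-specific introduction, so step 1 separates offer from assessment but does not mask it.

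**Cost.** An edit to the protocol and training, one data field, brief training of the second worker on the 13 items, and some added time in that worker's TB-screening workflow, which runs in parallel with testing. No added staff or visits.
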